# 1. Version History

Version	Summary of Changes	Details of Author
1.0	Not applicable, new document	

# 2. Glossary

Term	Definition
AEMPS	Spanish Agency of Medicines and Medical Devices
AF	Advance Event
AE	Adverse Event
SAE	Serious Adverse Event
EC	Ethics Committee
CRF	Case Report Form
AF	Atrial Fibrillation
CIP	Clinical Investigation Plan

# 3. Synopsis

TITLE	Prospective observational study of pulmonary vein cryoablation in subjects with Atrial Fibrillation (AF) in Spain.	
Type of Study	Post-market non-interventional study	
Study Product Name	Arctic Front Advance® cryoballoon connected to a nitrous oxide conveying system and inserted through a steerable sheath (FlexCath Advance®) from Medtronic. The device is CE marked and will be used according to the IFU for the pulmonary vein cryoablation. In accordance with standard clinical practice, any devices available on the market at that time with the CE mark and having the indication of pulmonary vein cryoablation may also be used.	
Sponsor	Medtronic Ibérica S.A., [name] (Spain)	
Indication under investigation	Pulmonary vein cryoablation in subjects with AF	
Investigation Purpose	To reflect on standard clinical practice in pulmonary vein cryoablation in Spanish hospitals, the different procedure protocols, details of intervention, complications, long-term follow-up strategy and results in these subjects.	
Product Status	The medical device has the CE mark and will be used according to the authorized instructions for use	
Primary Objective	Evaluate the efficacy of the cryoablation procedure at 12 months, defined as the absence of recurrences of atrial fibrillation	
Secondary Objectives	
 
Description of the profile of subjects who undergo this type of procedure (demographic factors, cardiovascular risk factors, medication, physical activity, sleep apnea, alcohol, smoking, chronic pulmonary disease, obesity, etc.).
 
To evaluate the acute efficacy of the procedure: complete isolation of the pulmonary veins demonstrated by the successful electrical disconnection of the pulmonary veins in the cryoablation procedure.
 
Description of the complications related to the procedure.
 
To evaluate the use of healthcare resources which this cryoablation procedure entails.
 
 ANCILLARY Objectives The participating sites may send proposals for additional analyses over the course of the study as long as they do not interfere with the primary objectives.	

Study Design	Observational, prospective, national multicenter study			
Sample Size	The observational study plans to enroll around 1000 subjects in approximately 30 Spanish sites. The enrollment period will be 2 years plus a minimum of 1 year of follow-up, with the possibility to extend it.			
Inclusion/Exclusion Criteria	Inclusion Criteria			
	Signature of the Data Release Form			
	■ Subjects ≥ 18 years old			
	
 
Subjects who meet the indication for the cryoballoon ablation procedure, in accordance with current guidelines for standard clinical practice.
 
			
	Exclusion Criteria			
	
 
Subjects with a life expectancy of less than 12 months.
 
Subjects who meet the exclusion criteria defined by local legislation (e.g., age, pregnancy, breastfeeding, etc.).
 
Subjects who may currently be enrolled, or who plan to take part, in a study with a drug or device that may cause bias during the course of this study. Co-participation in concurrent trials is only allowed when documented pre-approval is obtained from the Medtronic study manager
 
			
Study Procedures	Clinical data will be collected at the baseline procedure and at the annual follow-up. There are no associated additional tests and only the necessary data will be collected in accordance with the variables taken into account in the Case Report Form.			
Safety Assessments	The products used have the CE mark and are used according to the authorized indications for use. However, it is the investigator's responsibility to comply with any requirements for the reporting of Adverse Events (AE) as required by the Clinical Investigation Plan, by local legislation, and the specific requirements of each EC.			
	Product experiences will be reported in accordance with the monitoring system through the regular channel from the vigilance system.			
Statistics	The quantitative variables are expressed as mean, median, typical deviation and interquartile range depending on which is most suitable for the distribution of values. The differences between groups in relation to the quantitative variables will be evaluated through the student t test for independent samples or the analysis of variance (depending on the number of groups compared) and between variables through the student t test for related samples or the analysis of variance of repeated measures, as applicable.			
	The intermediate statistical reports proposed by the investigators will depend on the hypotheses suggested by the investigator.			

A nominal	significance	of a=0.05	will be	assumed	for a resu	ult to	be
	statistically				analysis	will	be
achieved us	sing the statis	stical packet	SPSS 2	.0.0.			

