#### 5.1.2. Secondary Objectives

- Description of the profile of subjects who undergo this type of procedure (demographic factors, cardiovascular risk factors, medication, physical activity, sleep apnea, alcohol, smoking, chronic pulmonary disease, obesity, etc.).
- To evaluate the acute efficacy of the procedure: complete isolation of the pulmonary veins demonstrated by the successful electrical disconnection of the pulmonary veins in the cryoablation procedure.
- Description of the complications related to the procedure.
- To evaluate the use of healthcare resources which this cryoablation procedure entails.

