#### Annual follow-up (+/- 28 days):

5.- Variables during follow-up: anti-arrhythmic treatment, clinical recurrence of arrhythmia, result of the continuous ECG monitoring, 12-lead ECG, Nuubo monitoring method, etc. according to the protocol for each site.

A blanking period of 3 months has been established.

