**TABLE 1: Data collection requirements** 

	Inclusion	Baseline visit	Procedure	Follow-up
IC signed and dated	x			
Subject demographics		X		
Medical history		X		
Cardiovascular medication		X		X
Echocardiography		X		
Pulmonary anatomy		X		
Procedure data			X	
AF monitoring test				x
Healthcare resource utilization			X	x
Adverse Events	When it occurs			
Study Exit	When it occurs			

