#### 9.6. Safety assessment

The products used have the CE mark and are used under the authorized indications for use according to their label. However, it is the investigator's responsibility to comply with any requirements for the reporting of Adverse Events (AE) as required by the Clinical Investigation Plan, by local legislation, and the specific requirements of each EC.

The investigators of this registry will report any deficiencies/malfunction and any adverse events related to the medical device through the regular channel from the vigilance system. As part of Medtronic's continual post-marketing safety assessment, Medtronic will evaluate those experiences and events and will produce monitoring reports for the local competent authorities as required.

In this registry, the adverse events will be reported through the eCRF. The investigator must enter all the information on the eCRF as soon as possible and before 10 calendar days from awareness date of the event, as long as the regulatory authorities do not require stricter timelines.

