## 11.2. Adverse Event and Device Defficiency reporting

The investigators of this registry will report any deficiencies/malfunction and any adverse events related to the medical device through the regular channel from the vigilance system. As part of Medtronic's continual post-marketing safety assessment, Medtronic will evaluate those experiences and events and will produce monitoring reports for the local competent authorities as required.

The investigator must notify the sponsor or its representative and the reviewing EC of any unexpected adverse event of the device, within 24 hours from awareness date.

In this registry, the adverse events will be reported through the eCRF. The investigator must enter all the information on the eCRF as soon as possible and before 10 calendar days from awareness date of the event, as long as the regulatory authorities do not require stricter timelines.

The following adverse events will be collected in this registry:

- Unanticipated Serious Adverse Device Events (USADE):
- All adverse events that lead to death.
- All adverse events related to the procedure (up to 30 days post-procedure), such as (non-exhaustive list):
  - Access site complications:
    - Arteriovenous fistula
    - Pseudoaneurysm
  - Endocarditis
  - Cardiac damage (including myocardial infarction)
  - Embolic complications (including stroke)
  - Tamponade (associated or not to urgent surgery)
  - Hemorrhage requiring transfusion
  - Temporal Paralysis of the phrenic nerve

Version 1.0 11/APR/2016

- Persistent Paralysis of the phrenic nerve
- Pulmonary vein stenosis
- Intense cephalea
- Hemoptysis
- Gastroparesis
- Mitral valve tearing
- Temporary STU elevation

Note: Early recurrences of AF/AFL/AT after the cryoablation process are to be expected. If these recurrences, which may require hospitalization of the subject or extension of his/her hospitalization, are within the "blanking" period, they will not be considered greater complications than the cryoablation procedure.

Note 2: temporal paralysis of phrenic nerve is defined as decrease in diaphragmatic excursion resolved prior to end of procedure. Detection of phrenic nerve damage prior to detectable decrease in diaphragmatic excursion during procedure will not be considered as AEs.

- All adverse events related to AF not related to the procedure (that appear after 30 days, throughout the study), which could be (non-exhaustive list):
  - Cardiovascular death
  - Systemic embolism

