## **Follow-up**

The Follow-up table contains clinical information related to the follow-up of the patient. At the time of writing this protocol, it is unknown whether a patient can have multiple follow-up visits.

Continuous variables will be described using the statistics of central tendency (mean and median), dispersion (minimum, maximum, standard deviation and interquartile range) and shape (skewness and kurtosis). The number of valid cases and the number of cases with missing values will be reported. The continuous variables in this table are: Date of the follow-up visit, Date of post-procedure discharge, Date of admission, Date of discharge, Number of hospital stays.

The categorical variables will be described by frequencies and percentages. The number of valid cases and the number of cases with missing values will be reported. The categorical variables contained in this table are: Follow-up visit, ECG record / Monitoring type, Recurrence 3 months post-procedure, Recurrence specification, Asymptomatic AF, Treatment, Antiarrhythmics, Antiarrhythmic type, Specify, Anticoagulants, NACOs type, REDO, Type REDO, Death, Hospital stay

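### Procedure complications count up to day 30, but no planned field separates no complication from status not known, so the reported percentage is a lower bound

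*Protocol*

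**What the plan says.** One secondary objective is "Description of the complications related to the procedure" (Protocol 5.1.2). Protocol 11.2 sets the window by listing, among the events to be collected, "All adverse events related to the procedure (up to 30 days post-procedure").

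The schedule after the procedure is thin. The synopsis says "Clinical data will be collected at the baseline procedure and at the annual follow-up". Section 9.1 gives the annual visit a window of 28 days either side, and Table 1 has one follow-up column. In that table adverse events belong to no visit; they are recorded "When it occurs". Under section 9.6 the investigator enters them "as soon as possible and before 10 calendar days from awareness date of the event", and section 11.2 repeats this.

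The SAP lists the variables form by form:
- Procedure contains a complications item, as does the procedure list in Protocol 9.1.
- Follow-up contains admission and discharge dates and the number of hospital stays, and its categorical list ends with "REDO, Type REDO, Death, Hospital stay". No complication item is listed.
- Adverse event holds reported events, with separate dates for the event and for when it became known. A patient may have none.
- Study exit holds only a reason and a date.

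For analyses over time, the SAP section on missing values carries the last valid status forward when event information is absent at database closure. Protocol 13 plans three analyses of the primary and secondary objectives: at the end of enrollment year 1, at the end of enrollment year 2, and at the end of follow-up.

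**The concern.** By choosing 30 days rather than discharge, the protocol makes post-discharge events part of the complication objective. No step in the plan establishes whether one occurred. The procedure form covers what happened up to its completion. After that, an event enters the database only if the site hears of it, and the reporting deadline does not start until it does.

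A subject with no adverse event form may therefore have had no complication, or may simply not have been asked about since discharge. The listed data cannot tell these two apart. The error runs one way: an unseen event can only lower the percentage. Most exposed are milder events without an admission, subjects lost before the annual visit, and the two analyses held while many annual visits are still to come.

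**Working it through.** The plan gives no complication rate, precision target or sample-size formula, so there is no figure to reproduce. The check has three parts.

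**1. Can the listed data show day-30 status?**
- In-procedure events: yes, through the complications item in the procedure data.
- Post-discharge events with an admission or death: partly, through the Follow-up fields, once that visit takes place.
- Post-discharge events without an admission: only if the site learns of them and completes an adverse event form.
- Subjects who leave early: Study exit has no event item. Protocol 9.9 allows removal for loss to follow-up after three failed contact attempts, without recording status to day 30.
- Remote review (Protocol 11.2) covers adverse event data already collected, so it cannot find an unreported event.

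**2. Timing.** Assume the procedure is close to enrollment and enrollment is uniform over two years (730 days).
- Annual visit: 365 − 28 = day 337 to 365 + 28 = day 393. This is 307 to 363 days after the 30-day window closes.
- End of enrollment year 1: past day 30, (365 − 30)/365 = 92%. Past a day-365 visit, 0%; if every visit fell on the earliest allowed day, (365 − 337)/365 = 7.7%.
- End of enrollment year 2: past day 30, (730 − 30)/730 = 96%. Past a day-365 visit, (730 − 365)/730 = 50%; with visits at day 393 or day 337, 46% or 54%.

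At the first analysis, then, the complication result rests almost entirely on the procedure form and on events that happened to come to the site's notice.

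**3. Size.** Let p be the true 30-day rate, s the share of complications first appearing after discharge, and m the share of those never reported. Then

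reported rate = p × (1 − s × m), and relative understatement = s × m.

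All three inputs are assumptions: p of 3%, 5% and 8%; s from 20% to 50%; m from 10% to 50%. The smallest understatement is 0.20 × 0.10 = 2% and the largest is 0.50 × 0.50 = 25%. Expected counts in 1000 subjects:

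| True rate | True events | Reported at 2% loss | Reported at 25% loss |
|---|---|---|---|
| 3% | 30 | 29.4 | 22.5 |
| 5% | 50 | 49.0 | 37.5 |
| 8% | 80 | 78.4 | 60.0 |

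For scale, the exact (Clopper-Pearson) 95% interval for 50 events in 1000 is 3.7% to 6.5%. In most combinations the interval around the reported rate still covers the true rate: 38 events in 1000 gives 2.7% to 5.2%, which includes 5%. In the worst combination tried, 60 reported against 80 true, it is 4.6% to 7.7% and excludes 8%.

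**The case against.** The strongest reply is that the plan provides for late discovery. The 30-day limit applies to the event, not to its reporting, and the SAP keeps the event date apart from the date of knowledge. A day-10 complication learned of at month 12 still has to be entered. Admissions and deaths have a second route through the annual form. Temporary phrenic paralysis, as Protocol 11.2 defines it, resolves before the procedure ends and so cannot fall in the gap. All of this stands, and it confines the problem to events never learned of, or not yet learned of at the time of analysis.

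A reader might infer that every event treated at another hospital, or resolved before month 12, is lost. The documents do not support that, because such an event can surface at the annual visit or in the records. Nor do they support assuming that most post-discharge events go unseen, for example 75%, given the admission and death fields. A reader might also infer that sites with closer early follow-up will look less safe. Follow-up practice does differ between sites, but no site comparison of complications is specified.

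It is also fair to say that the eCRF is not among the documents. The follow-up list in Protocol 9.1 is open-ended, the SAP does not know whether a patient can have several follow-up visits, and the content of the edit checks is not stated. A day-30 item could exist unlisted. Finally, no passage says outright that no form means no complication. That reading follows from an adverse event table holding only reported events, the absence of a listed status field, and the carry-forward rule. Neither document sets a denominator of subjects with verified status that would prevent it.

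**Conclusion.** The point holds as a limited, one-directional undercount in a secondary objective. The primary objective is not affected. As planned, the complication percentage is a lower bound: in-procedure events plus later events that came to the site's knowledge. Its shortfall is probably largest at the first two analyses, before most or many annual visits. At the end of follow-up, what remains is events never learned of.

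The size cannot be derived from the documents. Under the assumed ranges the relative understatement is about 2% to 25%, and in most of those scenarios the 95% interval still covers the true rate. The stronger conclusion that complications generally go uncaptured is not supported, since the procedure form and the awareness-based route both work for the events they reach. The defect is that a reader of the results could not tell how many subjects were known to be free of complications at day 30.

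**What to change.** 1. Add an edit check under Protocol 15.2. When the Follow-up form shows an admission or death dated within 30 days of the procedure and there is no matching adverse event form, raise a query. It should not force a form, because the admission may be planned or unrelated. The dates needed are already collected.
2. Add one item to the Follow-up and Study exit forms: any procedure-related event of section 11.2 up to day 30, answered yes / no / not known, with the date to which this was verified. It is completed from existing records or usual contact, so it adds no visit or test and fits the non-interventional design.
3. In the SAP, report the complication percentage over all ablated subjects together with the number whose day-30 status was verified. Show not known as its own category, and state that the carry-forward rule does not apply to this outcome. Label the two earlier analyses as reported complications only.

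The cost is one eCRF item, one edit check and a little extra data entry. The reported rate may rise slightly, and some subjects will appear as unknown.

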## 4. Introduction

## 4.1. Background

Atrial fibrillation (AF) is the most common clinical arrhythmia in the general population. Its prevalence increases with age and other cardiovascular risk factors and its morbi-mortality is considerably high, which implies a significant cost to health. Given the characteristics of the current population, AF is considered one of the most significant cardiovascular health problems that could become a pandemic in the 21st century.

Since 1998, when Haïssaguerre et al described how ectopic heartbeats originating in the pulmonary veins were the main trigger of atrial fibrillation (AF), treatment with curative expectations of these subjects focused on electrical isolation of the pulmonary veins. For this, different procedures and sources of energy were designed, of which point-by-point radiofrequency has been the most extensive technique up until now. However, pulmonary vein ablation with radiofrequency is a very laborious technique and not without complications. With the intention of facilitating the procedure, different techniques have been developed that try to isolate the pulmonary veins with a single application ("single-shot" devices). Of these devices, pulmonary vein cryoballoon ablation is the technique that has gradually been established in recent years as a more extensive alternative to radiofrequency ablation and with excellent long-term results in different published series in subjects with paroxysmal AF. In these subjects, cryoablation seems to be at least as effective and safe as radiofrequency ablation, requiring less training time and a shorter time for the procedure and exposure to radioscopy.

However, despite being a successful emerging technique, there are not many multicenter studies and Registries. Of those, the German cryoablation registry and the Freeze registry and its sub-studies stand out, in which several European sites took part (mainly German sites). In Italy, sets of subjects with paroxysmal and persistent AF have been reported sporadically, however there is no multicenter registry that describes the characteristics of the subjects who have undergone to AF cryoablation and the long-term results of these subjects.

#### 4.2. Device information

The Arctic Front Advance® connected to a nitrous oxide conveying system is used for pulmonary vein cryoablation which is inserted through a steerable sheath (FlexCath Advance®). The system progresses to the pulmonary vein ostium through a single transseptal catheterization and the balloon impacts against the venous ostium. When the nitrous oxide circulating through the system in a liquid state is released into the inside of the balloon through 8 ejectors, it leads to the switch from a very high pressure system to a very low pressure system. The sudden decompression of nitrous oxide in a liquid state means that it is transformed into a gas, causing a powerful endothermic reaction that absorbs heat from the adjacent tissues (*Joule-Thompson effect*). This reaction is the basis of the lesion caused by cryotherapy. Aerated and reheated nitrous oxide returns to the console through a connected vacuum system. For the registration of pulmonary vein potentials in real time, a circular octapolar electrode catheter (AchieveTM) is used during the ablation with an interelectrode distance of 4-6 mm (depending on the diameter of the catheter) which is inserted through the lumen of the balloon. The special configuration of the AchieveTM catheter with a rigid proximal consistency 0.9 mm diameter high supporting guidewire, can be used as a supporting guidewire for the balloon on the one hand and as a mapping and stimulation electrode on the other.

Currently at least 2 applications of cryothermia through the pulmonary vein with a duration of 180 seconds are recommended. However, you need to keep in mind that the dosing recommendations are based on data from former investigational studies of focal cryoablation. It is obvious that none of the tissue properties, the technology, or the coolants that were used are the same as those used nowadays for pulmonary vein cryoablation. This has meant that, despite the recommended application parameters, new protocols have been trialled with shorter application times and a lower number of applications per vein. The reduction in the application times of cryothermia seems to also reduce some of the complications arising from the technique such as phrenic paralysis, a circumstance which occurs more frequently after the first minute of application and during extra application after the disconnection.

If, as in the cryoablation procedure, there are differences in the protocol between sites, there is also diversity in terms of the follow-up of these subjects. At some sites, monitoring systems are used that vary between ones of very low sensitivity (24-hour Holter monitor) and those that use high-sensitivity devices such as implantable event recording systems.

To carry out the observational study, the devices mentioned previously will be used as well as future models that obtain the CE mark and are available on the market throughout the study, and that can be used in accordance with standard clinical practice.

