# 5. Study objectives and endpoints

## 5.1. Objectives

#### **5.1.1.** Primary Objective

To evaluate the efficacy of the cryoablation procedure at 12 months, defined as the absence of recurrences of atrial fibrillation.

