# 9. Study Procedures

It is an observational study whereby the participating sites will carry out the cryoablation procedure in accordance with standard practice at their site. During this baseline procedure and during follow-up, there are no related additional tests and only the data deemed necessary according to the Case Report Form will be collected.

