# 13. Statistical design and methods

The following statistical analysis plan of the data will be carried out:

The variables analyzed will be those collected in the subject registry corresponding to the different protocols of the procedure, intervention data, complications, follow-up and long-term results in these subjects. In the Method section there is a list of variables of interest.

Recurrence of AF will be defined as a clinically diagnosed episode of AF and accordingly documented (on ECG, Holter monitor with a duration of at least 30 seconds or implantable devices or event recording systems).

It is expected to carry out 3 analyses of the primary and secondary objectives described in the Clinical Investigation Plan:

- 1. At the end of the first year of enrollment
- 2. At the end of the second year of enrollment
- 3. At the end of follow-up

On the other hand, there will be 4 analyses of additional proposals throughout the study (see Appendix B: Publications Plan)

- Two analyses at the end of enrollment.
- Two analyses at the end of follow-up.

Each of the variables of interest will be described univariantly and individually.

Crosses of variables will also be carried out to describe each one of the clinical strata of interest.

When it is possible and of interest for the investigators, statistical comparisons between strata will be carried out through statistical tests.

Specific statistical models to respond to the interests of the investigators will be proposed, such as comparison of the procedures or comparison of subject strata.

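### The 12-month efficacy percentage pools very low- and high-sensitivity AF monitoring, and no recurrence analysis is stratified or adjusted for monitoring type or site

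*Protocol*

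**What the plan says.** - **Objective.** Protocol 5.1.1: "To evaluate the efficacy of the cryoablation procedure at 12 months", meaning absence of AF recurrence.
- **Monitoring.** Protocol 4.2 states that "there are differences in the protocol between sites, there is also diversity in terms of the follow-up of these subjects". It adds that at some sites "monitoring systems are used that vary between ones of very low sensitivity (24-hour Holter monitor) and those that use high-sensitivity devices", giving implantable recorders as the example of the latter. Section 9 says "there are no related additional tests", and the annual follow-up text in 9.1 has monitoring results collected "according to the protocol for each site".
- **Endpoint.** Protocol 13: "Recurrence of AF will be defined as a clinically diagnosed episode of AF and accordingly documented". ECG, Holter, implantable devices and event recorders all count as documentation. The SAP (Statistical models) repeats this and takes recurrences from both the Follow-up and the Adverse Event tables.
- **Analysis.** The SAP (Statistical models) gives one number and percentage free of recurrence at 12 months. It then compares subjects with and without recurrence by t and chi-squared tests, proposes logistic models if differences appear, and describes time to recurrence by Kaplan-Meier. No covariates are listed.
- **Related provisions.** Protocol 13: "Crosses of variables will also be carried out to describe each one of the clinical strata of interest". It also plans models "such as comparison of the procedures or comparison of subject strata". The SAP (Follow-up) collects monitoring type and asymptomatic AF, to be summarised by frequencies and percentages.

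**The concern.** A recurrence counts only if someone detects it, and the protocol itself says that the means of detection differ widely. Two registries with the same true efficacy and different monitoring mixes would report different percentages. The confidence interval does not show this, and enrolling more subjects would not reduce it.

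The second issue concerns the search for predictors. Procedure protocols also differ between sites, and comparison of procedures is a planned analysis. A factor that is fixed for a whole site carries with it everything else particular to that site, monitoring included. Tests that treat subjects as independent ignore this. These same unadjusted comparisons decide whether logistic models are proposed.

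**Working it through.** The documents give no expected recurrence rate, no sensitivities and no monitoring shares, so there is no plan figure to reproduce. Only the size (about 1000 subjects, about 30 sites, hence about 33 per site) and the 0.05 level come from the plan. Everything else below is assumed; tests are taken as two-sided.

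**1. Pooled percentage.** Let R be true recurrence, m the share of subjects on sensitive monitoring, and s_hi and s_lo the detection probabilities.

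Observed freedom = 1 − R × [m × s_hi + (1 − m) × s_lo]

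With R = 0.30, s_hi = 0.95, s_lo = 0.55 (true freedom 70%):

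| m | Observed freedom |
|---|---|
| 0 | 83.5% |
| 0.3 | 79.9% |
| 0.5 | 77.5% |
| 1 | 71.5% |

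The slope is 0.30 × 0.40 × 0.10 = 1.2 points per 10-point change in mix. Going from 30% to 50% moves the figure 2.4 points. The 95% half-width at n = 1000 is 1.96 × √(0.799 × 0.201/1000) = 2.5 points.

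**2. What shrinks the effect** (gap between all-low and all-high monitoring):
- Base case: 0.30 × 0.40 = 12 points.
- Half of the extra device-detected episodes are clinically diagnosed: s_hi = 0.55 + 0.5 × 0.40 = 0.75; gap 0.30 × 0.20 = 6.
- Adverse event forms capture half of the missed recurrences: 0.975 versus 0.775; gap 6.
- Both: 0.875 versus 0.775; gap 3.
- None of the extra episodes is clinically diagnosed: gap 0.

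With s_hi = 0.95, varying R from 0.20 to 0.40 and s_lo from 0.5 to 0.7 gives an extreme gap between 0.20 × 0.25 = 5 and 0.40 × 0.45 = 18 points.

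**3. Factors with no true effect.** Simulation of 30 sites of 33 subjects, sensitivities 0.95/0.55, sensitive monitoring at 3, 6 or 9 sites, and the factor allocated independently of monitoring. False-positive rates at nominal 0.05:

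| Setting | Unadjusted | Stratified by site monitoring class |
|---|---|---|
| Patient-level factor | 0.05 | 0.04–0.06 |
| Site-level factor, no other site differences | 0.08, 0.12, 0.13 | 0.04–0.06 |
| Site-level factor, other site differences (log-odds SD 0.3) | 0.12, 0.15, 0.17 | 0.08–0.11 |
| Site-level factor, SD 0.3, identical monitoring everywhere (0.70) | 0.09–0.10 | not applicable |

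The last two rows show that unequal monitoring adds to the excess but is not its only source. Stratifying by monitoring class alone does not restore 0.05 once sites differ for other reasons.

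**4. Which monitoring variable to use.** Suppose 10% have routine sensitive monitoring, symptoms occur in 60% of recurrent and 20% of non-recurrent subjects, and half of symptomatic subjects are moved to sensitive monitoring. Recorded sensitive monitoring then applies to 0.10 + 0.90 × 0.5 × 0.6 = 0.37 of recurrent and 0.10 + 0.90 × 0.5 × 0.2 = 0.19 of the others.
- By recorded type, sensitive: 1 − (0.30 × 0.37 × 0.95)/(0.30 × 0.37 + 0.70 × 0.19) = 1 − 0.1055/0.244 = 57%. Low: 1 − (0.189 × 0.55)/0.756 = 86%.
- By the site's routine practice: 1 − 0.30 × 0.95 = 71.5% versus 1 − 0.30 × (0.3 × 0.95 + 0.7 × 0.55) = 79.9%.

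Recorded type exaggerates the contrast because symptoms lead to closer monitoring.

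**The case against.** The registry sets out to describe standard practice, and the Synopsis includes follow-up strategy in that purpose. The percentage has no comparator and no success threshold. Protocol 13 allows crosses by strata of interest, the SAP explores differences in patient follow-up, and monitoring type is collected. Section 4.2 is background text that gives no shares. The definition needs a clinically diagnosed episode, and adverse event forms (Protocol 11.2) offer a second route to recurrences.

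Most of this stands. It makes the pooled figure legitimate and its dependence on mix possibly small. It does not close the gap: the permissive wording commits to nothing, and a univariate test of monitoring type would neither qualify the headline percentage nor adjust any other comparison.

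A reader might infer more, namely that unequal monitoring will turn procedure factors into false predictors. The documents do not support that. They say that procedures and follow-up both vary between sites, not that they vary together. In the simulation patient-level factors stay at 0.05, and the excess for site-level factors is largely a clustering effect that appears even when monitoring is identical.

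**Conclusion.** The omission is certain: no analysis of recurrence is stratified by or adjusted for monitoring type or site, although the protocol describes wide differences in monitoring. The pooled percentage can stand as freedom from detected, clinically diagnosed AF under usual care. It cannot be read as efficacy alone.

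Its sensitivity to the mix cannot be sized from the documents. The 1.2 points per 10-point change rests wholly on the assumed 30% recurrence and 0.95/0.55 detection. Under those values the extreme gap runs from 12 points down to 0, depending on clinical diagnosis and adverse event capture, so it would be wrong to quote 12 points as the bias.

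The error-rate point is secondary. It applies to factors set by whole sites, and its cause is that the tests ignore site, with differing monitoring as one contributor. The registry remains valid; this is a change that should be made for its results to be interpretable.

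**What to change.** In the SAP, Statistical models:

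1. Describe the pooled figure as freedom from detected, clinically diagnosed AF under usual-care monitoring.
2. Also report the 12-month result by monitoring class. Use the site's usual practice where known, with a mixed class where there is no single routine. Give the recorded type as a second table, with a rule for subjects with several types or visits and the caveat that symptom-prompted monitoring inflates recurrence in the sensitive stratum.
3. Stratify or adjust the recurrence comparisons, logistic models and Kaplan-Meier curves by monitoring class, and also account for site by a random effect or cluster-robust errors.
4. Report by class how many recurrences came only from the Adverse Event table and how many were recorded as asymptomatic, to show how much of any gap may come from detection.

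**Cost.** SAP wording, a few tables and possibly one question per site. Recorded type is already collected. Site is not among the Inclusion variables listed in the SAP, but the subject code is site-specific (Protocol 8.1). Intervals will widen, and sensitive strata may be small: with 3, 6 or 9 such sites (99, 198 or 297 subjects), 1.96 × √(0.715 × 0.285/n) gives half-widths of 8.9, 6.3 or 5.1 points. Under-detection within low-sensitivity strata remains.
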